9.2. Analysis of Safety Endpoints

- Adverse events, concomitant medications, laboratory safety tests, physical and neurological examinations, vital signs, electrocardiogram (ECG), and the anti-drug antibody test will be collected for each subject during the study according to the Schedule of Assessments. Standard safety reporting tables will summarize and list the safety data.
- Adverse events of interest and common adverse events will be summarized using Risk Differences between each tanezumab group and the celecoxib group, together with 95% confidence interval, using exact methods.
- Separate adverse event summaries by treatment group for adverse events of decreased sympathetic function will be conducted. More specifically, adverse events with the following preferred terms will be considered to represent adverse events of decreased sympathetic function: Blood pressure orthostatic decreased, bradycardia, dizziness postural, heart rate decreased, orthostatic hypotension, presyncope, sinus bradycardia, syncope, anhidrosis, hypohidrosis, abdominal discomfort, diarrhea, early satiety, fecal incontinence, nausea, vomiting, ejaculation delay, ejaculation disorder, ejaculation failure, hypertonic bladder, micturition urgency, nocturia, urinary frequency, urinary hesitation, urinary incontinence, respiratory distress and respiratory failure. If

² Details are described in [section 9.2](#).

necessary, this list of preferred terms may be adjusted for updates made to the MedDRA dictionary versions used for reporting.

- In addition to summaries of adverse events considered to represent adverse events of decreased sympathetic function noted above, adverse events of syncope, bradycardia, orthostatic hypotension, anhidrosis, or hypohidrosis are designated as adverse events of interest that will be reviewed by the unblinded E-DMC (See Section 9.6).
- Incidence of orthostatic hypotension using postural changes in blood pressure, in addition to mean changes in postural blood pressure will be summarized.
- The SAS scores will be summarized by treatment group for the total number of symptoms reported and total impact score. The summary will be shown by visit, and for the change from Baseline.
- The NIS is the sum of scores over all 37 items from both the Left and Right side. The change from baseline to each post-baseline visit in the NIS will be summarized. The change from Baseline to each study visit, and to Worst (largest) change from Baseline (over all post-Baseline visits) will be summarized.
- The neurological consultation data will be summarized all subjects, and for subjects with adverse events of abnormal peripheral sensation, which are described in the Neurological Examination Section (Section 7.3.9). The “conclusion from the neurological examination” data will be summarized for each timepoint, and as well as a summary of the final assessment over all neurological examinations for each subject.
- The incidence of subjects with any of the joint safety adjudication outcomes of rapidly progressive osteoarthritis (type-1 and type-2), subchondral insufficiency fracture (or SPONK), primary osteonecrosis, or pathological fracture will be shown by number of subjects treated and subject years of exposure (treatment plus follow-up periods), for individual treatment groups and differences between tanezumab treatment groups and the celecoxib treatment group. The risk ratio and risk difference with 95% Confidence intervals will be calculated for the comparisons of each tanezumab group versus the celecoxib group. The time to each event will be summarized, and (where there are sufficient numbers of subjects) Kaplan-Meier estimates of the time to event will be produced.
- The incidence of subjects with any of the joint safety adjudication outcomes of rapidly progressive osteoarthritis (type-2), subchondral insufficiency fracture (or SPONK), primary osteonecrosis, or pathological fracture will be analyzed as described above. In addition the same analysis will be performed for the individual events of all-cause Total Joint Replacements, and adjudicated outcomes of rapidly progressive osteoarthritis (type 1, type 2 and both types 1 and 2 combined), subchondral insufficiency fracture (or SPONK), primary osteonecrosis and pathological fracture.

- A listing of the subjects who develop anti-tanezumab antibodies after treatment for each dose, and the proportion of subjects who develop anti-tanezumab will be summarized for each dose.
- The PK profile will be examined for subjects with anti-tanezumab antibodies.
- Individual subjects with positive ADA results will be evaluated for potential ADA impact on the individual's efficacy and safety profile.

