7.4.3. Orthostatic Hypotension and Sympathetic Function Adverse Events

Blood pressure changes meeting the pre-specified criteria for orthostatic hypotension and confirmed as described in Section 7.3.5.1 will be designated as confirmed orthostatic hypotension episode and should be reported as an adverse event whether or not the subject had accompanying symptoms.

Confirmed episodes of orthostatic hypotension: If a confirmed episode of orthostatic hypotension occurs (as defined in Section 7.3.5.1) it should be reported as an adverse event and the subject should be further evaluated as described below to determine if a neurology or cardiology consultation should be obtained and/or whether further treatment with investigational product should occur. Figure 6 provides a flow diagram for the processes described below.

1. If no apparent medical cause (eg, dehydration, illness, medications) is identified at the time the orthostatic hypotension criterion is met and the subject is symptomatic, the subject should be further evaluated for the presence of sympathetic autonomic neuropathy by a cardiologist or neurologist as soon as possible. See “Sympathetic function adverse events” below for decisions regarding subject management and continued dosing with investigational product.
2. If an apparent medical cause is identified at the time the orthostatic hypotension criterion is met or if subject is asymptomatic, the subject should have a repeat assessment of orthostatic hypotension performed at least 1 week later but not more than 4 weeks later. During this time the investigator should attempt to address the underlying medical cause of the orthostatic hypotension. If confirmed orthostatic hypotension (as defined in Section 7.3.5.1) is present at the follow-up visit, the subject should be further evaluated for the presence of sympathetic autonomic neuropathy by a cardiologist or neurologist as soon as possible. See “Sympathetic function adverse events” below for decisions regarding subject management and repeat dosing.

[figure not shown]
Sympathetic function adverse events: Subjects reporting adverse events (any seriousness or severity) with preferred terms of bradycardia (see Section 7.3.6 for ECG criteria for

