3.5. Safety Endpoints

3.5.1. Adverse Events

An adverse event is considered treatment emergent relative to a given treatment if:

- The event occurs for the first time during the effective duration of treatment and was not seen prior to the start of treatment, or
- The event was seen prior to the start of treatment but increased in severity during treatment.

A 3-tier approach will be used to summarize AEs. Under this approach, AEs are classified into 1 of 3 tiers. Different analyses will be performed for different tiers (See [Section 6.1.1](#)).

Tier-1 events: These are pre-specified events of clinical importance. Tier-1 events include syncope, bradycardia, orthostatic hypotension, anhidrosis, hypohidrosis.

Tier-2 events: These are events that are not Tier-1 but are “common”. A MedDRA PT is defined as a Tier-2 event with a frequency of $\geq 3\%$ in any treatment group.

Tier-3 events: These are events that are neither Tier-1 nor Tier-2 events, and will be summarized using standard Pfizer data standards tables, where all Adverse Events will be included (ie, Tier-3 AEs will not be shown separately).

The adverse events of Abnormal Peripheral Sensation (APS) are defined in the table below.

| | |
|------------------------------|------------------------------------|
| Allodynia | Neuritis |
| Axonal neuropathy | Neuropathy peripheral |
| Burning sensation | Paraesthesia |
| Carpal Tunnel Syndrome | Paraesthesia oral |
| Decreased Vibratory Sense | Peripheral sensorimotor neuropathy |
| Demyelinating polyneuropathy | Peripheral sensory neuropathy |
| Dysaesthesia | Polyneuropathy |
| Formication | Polyneuropathy chronic |
| Hyperaesthesia | Sensory disturbance |
| Hyperpathia | Sensory loss |
| Hypoaesthesia | Thermohypoaesthesia |
| Hypoaesthesia oral | Sciatica |
| Intercostal neuralgia | Tarsal Tunnel Syndrome |
| Neuralgia | |

Adverse Events of Sympathetic Nervous System are defined in the table below.

| | |
|--------------------------------------|-------------------------|
| Abdominal discomfort | Micturition urgency |
| Anal incontinence | Nausea |
| Anhidrosis | Nocturia |
| Blood pressure orthostatic decreased | Orthostatic hypotension |
| Bradycardia | Pollakiuria |
| Diarrhoea | Presyncope |
| Dizziness postural | Respiratory distress |
| Early satiety | Respiratory failure |
| Ejaculation delayed | Sinus bradycardia |
| Ejaculation disorder | Syncope |
| Ejaculation failure | Urinary hesitation |

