6.1.1. Safety Measures: Adverse Events

Pfizer standard safety data presentations will be made for adverse event data.

The details of Tier-1, Tier-2 and Tier-3 AEs are described in [Section 3.5.1](#).

Treatment-emergent adverse events within Tier-1 will be summarized. The combined Tier-1 adverse events, but not each adverse event will be summarized using Risk Differences between each tanezumab group and celecoxib, together with 95% CI and p-value, using exact methods. Treatment-emergent adverse events within Tier-2 will be summarized using Risk Differences between each tanezumab group and celecoxib, together with 95% CI, using exact methods. There will be no multiplicity adjustment for these significance tests. These tables will be produced for the comparisons of tanezumab 5mg versus celecoxib and tanezumab 10mg versus celecoxib.

The following footnote will be used in the Tier-1 AE tables: “P-values and confidence interval are not adjusted for multiplicity and should be used for screening purpose only. 95% CIs are provided to help gauge the precision of the estimates for Risk Difference.” Similarly the following footnote will be used in the Tier-2 AE tables: “Confidence intervals are not adjusted for multiplicity and should be used for screening purpose only. 95% Confidence intervals are provided to help gauge the precision of the estimates for Risk Difference.”

It should be recognized that most studies are not designed to reliably demonstrate a causal relationship between the use of a pharmaceutical product and an adverse event or a group of adverse events. Except for select events in unique situations, studies do not employ formal adjudication procedures for the purpose of event classification. As such, safety analysis is generally considered as an exploratory analysis and its purpose is to generate hypotheses for further investigation. The 3-tier approach facilitates this exploratory analysis.

Pfizer standard safety data presentations will be made for demography data, concomitant medications, discontinuation data, adverse event data, laboratory test data, vital sign data and ECG data.

The non-standard safety tables as described in [Section 3.5.1](#) will also be summarized. The details are described below.

Summary of AEs, Incidence of AEs, Incidence of AEs leading to discontinuation and summary of Serious AEs will be shown for the whole study period (including the safety follow-up period) will be created.

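### The only pooled sympathetic risk difference versus celecoxib uses five single terms; three near-synonyms on the sponsor's own sympathetic list fall outside it, and the 27-term group has no between-arm estimate.

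*Protocol*

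**What the plan says.** **The five terms.** Protocol 9.2 states that "adverse events of syncope, bradycardia, orthostatic hypotension, anhidrosis, or hypohidrosis are designated as adverse events of interest". SAP 3.5.1 repeats them: "Tier-1 events include syncope, bradycardia, orthostatic hypotension, anhidrosis, hypohidrosis". Protocol 7.4.3 names the same five as coded terms ("with preferred terms of bradycardia" and the other four).

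**The wider list.** Protocol 9.2 also lists 27 preferred terms for decreased sympathetic function, beginning "Blood pressure orthostatic decreased, bradycardia, dizziness postural, heart rate decreased, orthostatic hypotension, presyncope, sinus bradycardia, syncope". SAP 3.5.1 has a 27-term list as well.

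**Which groups get a between-arm estimate.** Protocol 9.2: "Adverse events of interest and common adverse events will be summarized using Risk Differences between each tanezumab group and the celecoxib group". SAP 6.1.1 narrows this for the events of interest: "The combined Tier-1 adverse events, but not each adverse event will be summarized using Risk Differences between each tanezumab group and celecoxib", with an exact 95% CI and p-value. Tier-2 terms, meaning single MedDRA terms at 3% or more in any arm, get a risk difference one term at a time. SAP 6.1.1 adds: "These tables will be produced for the comparisons of tanezumab 5mg versus celecoxib and tanezumab 10mg versus celecoxib". The 27-term group gets incidence and severity tables only, with no risk difference or interval.

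**The concern.** Long-term safety is the primary objective, and sympathetic function is one of the two neurological safety questions used to justify the sample size. The between-arm estimate for it rests on five single terms. The sponsor's own list shows that a slow heart rate or a postural fall in blood pressure can also be coded as sinus bradycardia, heart rate decreased or blood pressure orthostatic decreased. No rule in either document brings those terms into Tier-1. With about 66 subjects per arm, a few events coded one way or the other can change the pooled estimate materially.

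The sample-size argument in Protocol 9.1 concerns the 27-term group (its footnote points to the list in 9.2). That group has no planned between-arm estimate.

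**Working it through.** **Inputs.** Arm size about 66, range 56 to 73 (Protocol 9.1). Assumed incidence 6% for the 27-term group in tanezumab subjects, with 113 tanezumab subjects at the lower enrolment limit and 170 combined with A4091059 (Protocol 9.1). Tier-2 cut 3% in any arm (SAP 3.5.1).

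**1. The plan's own figures.** Exact binomial, P(lo ≤ X ≤ hi):
- n = 113, p = 0.06: P(4 ≤ X ≤ 10) = 0.836.
- n = 170, p = 0.06: P(6 ≤ X ≤ 14) = 0.858.

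Both meet the stated 80%. The planning figures are sound, but they describe the 27-term group.

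**2. List comparison.** All five Tier-1 terms are on the SAP's 27-term list. That leaves 27 − 5 = 22 terms outside Tier-1, including the three near-synonyms.

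**3. What can miss every risk difference.** A term needs ceil(0.03 × n) subjects in some arm to reach Tier-2.

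| Arm size | Needed for Tier-2 | Most per term below the cut | Three terms together |
|---|---|---|---|
| 56 | 2 | 1 | 3 (5.4%) |
| 66 | 2 (2/66 = 3.03%) | 1 | 3 (4.5%) |
| 67 | 3 (2/67 = 2.99%) | 2 | 6 (9.0%) |
| 73 | 3 | 2 | 6 (8.2%) |

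These are ceilings, not forecasts. For scale, 6% of 66 is 0.06 × 66 ≈ 4 subjects for the whole 27-term group.

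**4. How often Tier-2 would catch one of these terms.** The documents give no incidence for them, so the true rate r is assumed, equal in all three arms. P(any arm) = 1 − [1 − P(X ≥ k)]³, where k is the count needed.

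| r | n = 66, k = 2 | n = 73, k = 3 |
|---|---|---|
| 0.5% | 1 − (1 − 0.0434)³ = 12.5% | 1.8% |
| 1% | 1 − (1 − 0.1414)³ = 36.7% | 10.7% |
| 2% | 1 − (1 − 0.3814)³ = 76.3% | 44.8% |

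Even when a term is caught, it gets its own estimate and is not added to the pool.

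**5. Effect on the pooled estimate.** If a fraction c of these events is captured in every arm, the observed risk difference is c × (true risk difference): smaller in size, same sign, and zero if the truth is zero. If capture or case mix differs by arm, then wider RD = five-term RD + RD of subjects who have only a near-synonym term. Assumed counts at 66 per arm, starting from 4 v 1 on Tier-1 (RD 3/66 = 4.5 points):
- three added on tanezumab only, 7 v 1: RD 6/66 = 9.1 points;
- three added on each arm, 7 v 4: RD 3/66 = 4.5 points;
- three added on celecoxib only, 4 v 4: RD 0.

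The pooled incidence can only rise when terms are added. The risk difference can move either way.

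**The case against.** **Reporting instructions.** Protocol 7.3.6 tells investigators to report ECG-criterion events as bradycardia, and Table 5 and 7.4.3 direct confirmed postural falls to orthostatic hypotension. This stands, and it makes heavy leakage less likely. It is still an instruction on reporting and not an analysis rule. The 7.3.6 instruction covers ECGs, scheduled at Screening and Weeks 16, 56 and 80. Pulse is taken at every clinic visit (7.3.5), where no term is prescribed. Neither document says how verbatim terms map to preferred terms.

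**Other analyses.** Orthostatic hypotension is summarised from measured blood pressure (SAP 3.5.3, 6.1.3), ECG heart rate is summarised (6.1.5), and sympathetic neuropathy is summarised from investigator and consultant assessment (6.1.8). The three terms appear in the 27-term tables. A reader might infer that these events are lost from the report. They are not: they leave the pooled estimate only. None of these summaries is a pooled risk difference with an interval.

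**Direction.** A reader might infer that the Tier-1 risk difference is biased low against tanezumab's true risk. The documents do not support that. Sites are blinded (Protocol 5.2), and 1.2.4.3 reports sympathetic event rates at 2.5 to 10 mg no higher than placebo or active comparator in Phase 3 osteoarthritis studies. Understatement of the difference requires a tanezumab excess in the excluded terms.

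**A dramatic example.** A split such as 6 v 0 (Fisher p = 0.028) cut to 3 v 0 (p = 0.24) is tempting but extreme. It puts 9.1% of one arm in a few terms, when 6% is assumed for all 27, and no events on celecoxib. A less extreme assumption, 6 v 2 cut to 3 v 1, gives p = 0.27 and 0.62. SAP 5.1 tests no hypotheses, and 6.1.1 limits these p-values to screening, so crossing 0.05 decides nothing.

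**Flexibility and coherence.** SAP 3.5.1 allows its lists to be updated, and the E-DMC looks beyond the five terms (Protocol 9.6). An optional update does not fix a grouping in advance, and E-DMC review does not alter the final analysis. The five terms match the evaluation triggers in 7.4.3, which is a good reason to keep them as Tier-1.

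**Conclusion.** The point holds as a gap in the planned estimates. The five-term Tier-1 pool is the only pooled sympathetic adverse-event risk difference against celecoxib. Three near-synonyms that the sponsor itself classes as sympathetic are outside it unless one alone reaches 3%. At about 66 per arm, up to three subjects per arm (one per term) can enter no risk difference; in arms of 67 to 73 the ceiling is six.

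The actual size is unknown. The step 4 probabilities and the step 5 counts rest on assumed rates and splits. What follows from the definitions is a lower pooled incidence wherever such events occur, less precision, and attenuation toward zero of any true difference when capture is equal across arms. The 27-term group behind the sample-size argument is left without any between-arm estimate. The change is worth making but does not threaten the trial's validity.

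**What to change.** Before unblinding, in SAP 6.1.1, keep the five-term Tier-1 analysis as it stands and add a risk difference with exact 95% CI, for each tanezumab group versus celecoxib, for:

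- (a) Tier-1 plus sinus bradycardia, heart rate decreased and blood pressure orthostatic decreased, counting each subject once;
- (b) the full 27-term sympathetic group.

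Both are needed. Group (b) matches Protocol 9.1, but it includes terms such as nausea, which 1.2.4.2 reports as more frequent on active comparator than on tanezumab in the osteoarthritis studies, so it could mask a cardiovascular signal. Group (a) is closer to the findings that Tier-1 is meant to capture.

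Fix the lists by preferred term in SAP 3.5.1, and add a matching line to Protocol 9.2 if it is amended. Leave Protocol 7.4.3 unchanged: it already agrees with Tier-1, and it governs dosing.

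Cost: a few lines of SAP text and a lookup of terms already listed. The downside is two more unadjusted, descriptive comparisons per tanezumab dose, which should carry the existing screening-purpose footnote.

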9.3. Analysis of Efficacy Endpoints

Efficacy endpoints regarding the continuous data will examine the change from Baseline to each timepoint (Week 2, 4, 8, 12 [LBPI score only], 16, 24, 32, 40, 48, 56 and 64) in LBPI score, RMDQ total score, Patient Global Assessment of Low back Pain and BPI-sf measures. The differences with 95% confidence intervals will be calculated for the comparisons of each tanezumab group versus the celecoxib group. Details for the missing handling will be documented in the Statistical Analysis Plan.

Subject response endpoints of improvement in the average LBPI score of ≥ 30 , 50, 70 and 90%, improvement in the Patient's Global Assessment of Low Back Pain ≥ 2 points and the Chronic Low Back Pain Responder Index will be summarized to Weeks 16, 24, 40 and 56. The differences with 95% confidence intervals will be calculated for the comparisons of each tanezumab group versus the celecoxib group. Details for the missing handling will be documented in the Statistical Analysis Plan. Cumulative average LBPI response at Week 16, 24 and 56 using response definitions from a reduction of $>0\%$ to $=100\%$ (in steps of 10%) will be summarized.

A two-way table showing number and percentage of subjects will summarize the response for each dimension (item) for the EQ-5D-5L at Baseline versus Weeks 16 and 56. These summary tables will be shown by treatment group. In addition, the EQ-5D-5L overall health utility score will be summarized for each treatment and for each time point assessed.

Summaries of the change from Baseline to Week 16, 56 and 64 or Early Termination in the WPAI:LBP impairment scores will be shown by treatment group.

All data from TSQM and mPRTI will be summarized by visit. The HCRU data will be reported as outlined in the SAP.

The incidence of and time to withdrawal due to lack of efficacy will also be summarized for discontinuations up to Week 16 and 56. Kaplan-Meier estimates of the time to discontinuation will be shown for selected percentiles, dependent on the level of discontinuation. The expectation is that these would be the 1st, 2nd, 5th, 10th and 25th percentiles. Other percentiles may be shown if the level of discontinuation due to lack of efficacy as calculated using Kaplan-Meier procedure is sufficiently large.

The incidence and number of days of rescue medication use will be summarized during Weeks 2, 4, 8, 12, 16, 24, 32, 40, 48, 56 and 64, and the amount of rescue medication taken in a week summarized during Weeks 2, 4, 8, 12 and 16.

For the efficacy analysis, the observed data (no imputation for missing data) will be summarized. Additional analyses may explore the sensitivity of the efficacy analysis results to missing data. The details will be provided in the Statistical Analysis Plan.

Any efficacy data collected at an Early Termination visit will be excluded from summary and analyses of efficacy with the following exception: Any efficacy data collected at the Early Termination visit for subjects that have discontinued the study early, and the observations are within 10 weeks after the last dose (8 weeks plus a window of 2 weeks) can be included in the efficacy summaries and analyses for the appropriate efficacy window in which the data falls.

